6.2.5. Day 3 - SAD

The following procedures will be completed:

- Obtain temperature, supine pulse and supine triplicate blood pressure. Blood pressure is the only vital sign to be collected in triplicate.

- Collect blood samples for pharmacokinetic analysis 48 hours after Day 1 dosing.
- Collect blood samples for FPG and fasting glucagon.
- Assess symptoms by spontaneous reporting of adverse events and by asking the subjects to respond to a non-leading question such as “How do you feel?”
- Record concomitant medications.

6.2.6. Day 4 - SAD

The following procedures will be completed:

- Obtain fasting weight.
- Obtain temperature, supine pulse and supine triplicate blood pressure. Blood pressure is the only vital sign to be collected in triplicate.
- Collect blood sample for fasting lipids.
- Collect blood sample for fructosamine and 1,5-anhydroglucitol.
- Collect blood sample for FPG, fasting glucagon and fasting GLP-1 (**SAD IV Cohort 5**).
- Collect blood sample for 72 hr PK analysis.
- Obtain fingerstick glucose before breakfast.
- Prior to MMTT, collect the time 0 minute fasting blood samples for FPG, C-peptide, insulin, glucagon and GLP-1 (**SAD SC Cohorts 1-4**).
- Administer MMTT in AM. (**SAD SC Cohorts 1-4**) Collect samples (glucose, C-peptide, insulin, glucagon and GLP-1) at:
 - 15 minutes (5 minutes after fluid meal is consumed which requires 10 minutes; See **Section 7.4.1.2**);
 - 30 minutes;
 - 60 minutes;
 - 120 minutes
 - 180 minutes;
 - 240 minutes.

- Obtain fingerstick glucose 2-hr post breakfast, before lunch, 2-hr post-lunch, before dinner, 2-hr post-dinner, prior to snack (between 9 and 10 pm).
- Assess symptoms by spontaneous reporting of adverse events and by asking the subjects to respond to a non-leading question such as "How do you feel?"
- Record concomitant medications.

6.2.7. Day 5 - SAD

The following procedures will be completed:

- Obtain fingerstick glucose at 0300 and before breakfast.

Prior to discharge from the clinical research unit:

- Conduct full physical exam.
- Obtain fasting weight.
- Collect triplicate 12-Lead ECG.
- Obtain temperature, supine pulse rate and supine triplicate blood pressure. Blood pressure will be the only vital sign to be collected in triplicate.
- Collect fasting blood and urine samples for safety labs.
- Collect blood samples for coagulation panel, amylase and lipase.
- Collect blood samples for FPG and fasting glucagon.
- Collect blood sample for 96 hr PK.
- Assess injection site (required if reaction was noted on Day 1).
- Assess symptoms by spontaneous reporting of adverse events and by asking the subjects to respond to a non-leading question such as "How do you feel?"
- Record concomitant medications.

If a subject has any clinically significant, study-related abnormalities at the conclusion of a scheduled inpatient portion of the study, the Pfizer medical monitor (or designated representative) should be notified and the subject may be asked to remain in the Clinical Research Unit until such abnormalities are deemed not clinically significant, or it is safe for outpatient follow-up. If the subject is unable or unwilling to remain in the Clinical Research Unit and/or when outpatient follow-up is deemed appropriate, the Pfizer medical monitor (or designated representative) should be so notified, and the investigator should make every

effort to arrange follow-up evaluations at appropriate intervals to document the course of the abnormalities.

6.2.8. Days 8 (± 1), 22 (± 1) and 43 (± 3) - SAD

The following procedures will be completed:

- Obtain temperature, supine pulse rate and triplicate supine blood pressure. Blood pressure will be the only vital sign collected in triplicate.
- Collect fasting blood and urine samples for safety labs.
- Collect blood samples for FPG and fasting glucagon (all cohorts).
- Collect blood sample for PK analysis.
- Assess symptoms by spontaneous reporting of adverse events and by asking the subjects to respond to a non-leading question such as "How do you feel?"
- Record concomitant medications.
- Confirm contraception method.

6.2.9. Days 15 (± 1) and 29 (± 2) - SAD

The following procedures will be completed:

- Conduct limited physical examination.
- Obtain fasting weight.
- Collect triplicate 12-Lead ECG.
- Obtain temperature, supine pulse rate and triplicate supine blood pressure. Blood pressure will be the only vital sign collected in triplicate.
- Collect fasting blood and urine samples for safety labs.
- Collect blood sample for fasting lipid profile.
- Collect blood sample for PK analysis.
- Collect blood sample for ADA analysis.
- Collect blood samples for fructosamine and 1,5-anhydoglucitol.
- Collect blood sample for HbA1c (Day 29 only).

- Collect blood samples for coagulation panel, amylase and lipase.
- Obtain fingerstick glucose before breakfast (MMTT).
- Prior to MMTT, collect the 0 minute timepoint fasting blood samples for FPG, C-peptide, insulin, glucagon and GLP-1.
- Administer MMTT in AM. Collect samples (glucose, C-peptide, insulin, glucagon and GLP-1) at:
 - 15 minutes (5 minutes after fluid meal is consumed which requires 10 minutes; See [Section 7.4.1.2](#));
 - 30 minutes;
 - 60 minutes;
 - 120 minutes;
 - 180 minutes;
 - 240 minutes.
- Obtain fingerstick glucose before breakfast, 2-hr post breakfast, before lunch, 2-hr post-lunch, before dinner, 2-hr post-dinner, prior to snack (between 9 and 10 pm).
- Assess symptoms by spontaneous reporting of adverse events and by asking the subjects to respond to a non-leading question such as “How do you feel?”
- Record concomitant medications.
- Question subject on metformin compliance.
- Confirm contraception method.

6.2.10. Day 16 (± 2) and Day 30 (± 2) - SAD

The following procedures will be completed by the subject at home, no clinic visit is required:

- Obtain fingerstick glucose at 0300 and prior to breakfast.

6.2.11. Day 57 (± 3) - SAD

The following procedures will be completed:

- Conduct limited physical examination.

- Obtain fasting weight.
- Collect triplicate 12-Lead ECG.
- Obtain temperature, supine pulse rate and triplicate supine blood pressure. Blood pressure will be the only vital sign collected in triplicate.
- Collect fasting blood and urine samples for safety labs.
- Collect blood sample for fasting lipid profile.
- Collect blood sample for PK analysis.
- Collect blood sample for ADA analysis.
- Collect blood samples for fructosamine and 1,5-anhydoglucitol.
- Collect blood sample for HbA1c.
- Collect blood samples for coagulation panel, amylase and lipase.
- Collect blood samples for FPG, fasting glucagon and fasting GLP-1.
- Assess symptoms by spontaneous reporting of adverse events and by asking the subjects to respond to a non-leading question such as “How do you feel?”
- Record concomitant medications.
- Question subject on metformin compliance.
- Confirm contraception method.

6.2.12. Day 85 (± 3)/Early Termination – SAD

The following procedures will be performed:

- Conduct limited physical exam of the skin, heart, lungs, abdomen and extremities by trained medical personnel at the investigator site.
- Assess temperature, supine pulse rate and triplicate supine blood pressure. Blood pressure will be the only vital sign collected in triplicate.
- Collect fasting weight and triplicate waist circumference.
- To measure waist circumference, use a spring-loaded tape measure, and starting at the top of the hip bone, bring it all the way around, level with the navel. Tape measure

should not be too tight and parallel with the floor. Instruct subject to not hold their breath. Measurement should not include navel.

- Collect triplicate 12-lead ECG.
- Collect fasting blood and urine samples for safety labs.
- Collect blood sample for fasting lipid profile.
- Collect blood sample for fructosamine and 1,5-anhydroglucitol.
- Collect blood samples for coagulation panel, amylase and lipase.
- Collect blood sample for HbA1c.
- Collect blood samples for FPG, fasting glucagon and fasting GLP-1.
- Collect blood sample for PK analysis.
- Collect blood sample for ADA analysis.
- Assess symptoms by spontaneous reporting of adverse events and by asking the subjects to respond to a non-leading question such as “How do you feel?”
- Record concomitant medications.
- Question subject on metformin compliance.
- Confirm contraception method.
- Schedule 1-3-month extended follow-up visit – site will be notified if visit will be required once data is available.

Note for extended follow-up: Subjects will continue to be monitored beyond the last scheduled visit, if necessary, for elevated glucagon levels and/or presence of anti-PF-06293620 antibodies (at approximately 1-3 month intervals) until their glucagon/ADA levels return to approximate baseline or establish a new steady-state level.

6.3. Study Procedures - MAD

For the study period described below, when multiple procedures are scheduled at the same time point(s) relative to dosing, the following chronology of events should be adhered to, where possible.

- ECGs: obtain prior to vital signs and as close as possible to scheduled time, but prior to blood specimen collection; all ECGs will be submitted to Central ECG vendor for

independent review. On dosing days, collect triplicate ECG prior to study drug administration (pre-dose) and 1, 2, and 4 hours after dosing.

- Blood pressure/pulse rate: obtain as close as possible to scheduled time, but prior to blood specimen collection.
- Pharmacokinetic blood specimens: obtain at scheduled time within 10% of the nominal time from dosing.
- Other procedures: obtain all other procedures as close as possible to the scheduled time, but may be obtained before or after blood specimen collection.

6.3.1. Day -3 (MAD)

Subjects will be admitted to the Clinical Research Unit. Subjects will be required to stay in the Clinical Research Unit for 5 nights and will be discharged on Day 3.

Site staff will review concomitant medications, adverse events and contraception method. Concomitant medications, including metformin compliance, will be recorded in medication history. Any noted adverse events will be recorded as prior medical history.

On admittance to the CRU, subjects will undergo the following procedures:

- Urine drug screen (for illicit drugs).
- Peripheral IV (PIV)/hep lock may be placed, in accordance with site policies, for serial blood collections on Day -2.
- Question subject on metformin compliance.
- Confirm contraception method.

6.3.2. Day -2 (MAD)

On Day -2, after an overnight fast of at least 10 hours, the following procedures will be performed:

- Assess symptoms by spontaneous reporting of adverse events and by asking the subjects to respond to a non-leading question such as "How do you feel?"
- Collect fasting weight.
- Assess patency of peripheral IV (PIV)/heplock, in accordance with site policies,
 - If no longer patent remove and insert a new PIV/heplock in accordance with site policies. Allow subject to rest at least 1 hour prior to obtaining vital signs and initiating 24 hour ambulatory blood pressure monitoring.

- Assess temperature, supine pulse rate and triplicate supine blood pressure. Blood pressure will be the only vital sign collected in triplicate.
- Initiate 24 hour ambulatory blood pressure monitoring.
 - Placement of cuff must not be on the same arm as the PIV.
- Initiate mean daily glucose profile.
 - Collect blood sample at the following timepoints: 30 minutes before and immediately prior to AM meal, 30, 60, 90, 120 and 180 minutes after the start of the AM meal; immediately prior to the midday meal, 60, 120 and 180 minutes after the start of the midday meal; immediately prior to the evening meal, 60, 120 and 180 minutes after the start of the evening meal; approximatey at 11:00 PM.
 - On days when mean daily glucose profiles are being collected meals will be given at approximately 08:00 AM, 12:00 PM and 6:00 PM. Subjects will have 30 minutes to finish the meal and must consume the entire meal. Collection times are from the start of the meal.
- Record concomitant medications.
- Question subject on metformin compliance.

6.3.3. Day -1 MAD

On Day -1, after an overnight fast of at least 10 hours, the following procedures will be completed:

- Assess symptoms by spontaneous reporting of adverse events and by asking the subjects to respond to a non-leading question such as “How do you feel?”
- Review medical history
- Assess patency of peripheral IV (PIV)/heplock, in accordance with site policies,
 - If no longer patent remove and insert a new PIV/heplock in accordance with site policies. Allow subject to rest at least 1 hour prior to obtaining vital signs.
- Obtain blood sample at approximately 03:00 AM and 07:30 AM (immediately prior to breakfast) to complete the mean daily glucose profile.
- Obtain temperature, supine pulse and triplicate supine blood pressure.
- Complete 24 hour ambulatory blood pressure monitoring.

- NOTE: Before proceeding with any other Day -1 assessments, immediately upload the Day -2 Ambulatory blood pressure monitoring (ABPM) data to the vendor to determine if the data passes vendor technical quality control (QC). If the data fails technical QC, immediately restart/repeat the ABPM on Day -1 to ensure a baseline/pre-dose dataset is obtained. Then start the remaining Day -1 procedures.
- Conduct limited physical exam of the skin, heart, lungs, abdomen and extremities by trained medical personnel at the investigator site.
- Collect fasting weight and triplicate waist circumference.
 - To measure waist circumference, use a spring-loaded tape measure, and starting at the top of the hip bone, bring it all the way around, level with the navel. Tape measure should not be too tight and parallel with the floor. Instruct subject to not hold their breath. Measurement should not include navel.
- Collect blood samples for the following:
 - Fasting serum chemistry;
 - Hematology;
 - Fasting lipid profile;
 - Apo B;
 - HbA1c;
 - Fructosamine;
 - 1,5-anhydroglucitol;
 - ADA;
 - Banked Specimen (Pharmacogenomics).
- Obtain fingerstick glucose before breakfast (fasting) before MMTT.
- Before MMTT, collect 0 minute fasting timepoint blood sample for FPG, C-peptide, insulin, glucagon and GLP-1 (all cohorts).
- Administer MMTT in AM; begin sample collection (glucose, C-peptide, insulin, glucagon and GLP-1):
 - 15 minutes from start of meal (first sample collected 5 minutes post meal; the liquid should take 10 minutes to consume; See **Section 7.4.1.2**);

- 30 minutes;
- 60 minutes;
- 120 minutes;
- 180 minutes;
- 240 minutes.
- Obtain fingerstick glucose measurements 2 hr post- breakfast, before lunch, 2-hr post-lunch, before dinner, 2-hr post-dinner, prior to snack (between 9 and 10 PM).
- Record concomitant medications.
- Question subject on metformin compliance.
- Randomize subject to study treatment.

6.3.4. Day 1 - MAD

On Day 1, after an overnight fast of at least 10 hours, the following procedures will be completed **Prior to dosing**:

- Obtain finger-stick glucose measurement at 0300.
- Assess symptoms by spontaneous reporting of adverse events and by asking the subjects to respond to a non-leading question such as “How do you feel?”
- Assess patency of peripheral IV (PIV)/heplock, in accordance with site policies.
 - If no longer patent remove and insert a new PIV/heplock in accordance with site policies. Allow subject to rest at least 1 hour prior to obtaining vital signs and initiating 24 hour ambulatory blood pressure monitoring.
- Collect triplicate 12-Lead ECG.
- Collect temperature, supine pulse and triplicate supine blood pressure.
- Obtain finger-stick glucose measurement prior to breakfast (fasting).
- Obtain fasting weight.
- Collect a blood sample for pharmacokinetic analysis (pre-dose).
- Collect blood samples for the following:
 - Hematology;

- Fasting clinical chemistry;
- Coagulation panel, amylase and lipase.
- Collect blood for FPG, fasting glucagon and fasting GLP-1.
- Collect urine for urinalysis (clean catch, midstream).
- Initiate 24 hour ambulatory blood pressure monitoring (at least 1 hour prior to study drug administration).
 - Placement of cuff must not be on the same arm as the PIV.
- Administer the study medication (see **STUDY TREATMENTS** and **Administration Sections**).

After dosing, the following procedures will be completed:

- Assess temperature, supine pulse rate and triplicate supine blood pressure at 1, 2, and 4 hours after dosing. Blood pressure is the only vital sign to be collected in triplicate.
- Obtain triplicate 12-lead ECG measurements at 1, 2, and 4 hours after dosing.
- Collect blood samples for pharmacokinetic analysis at 1 and 4 hours following dosing.
- Injection site assessment immediately after injection at: 15 and 30 minutes, 1, and 2 hours post administration. Additional assessments should be performed as needed after the last assessment of 2 hrs post-dose on dosing days.
- Record concomitant medication.
- Assess symptoms by spontaneous reporting of adverse events and by asking the subjects to respond to a non-leading question such as “How do you feel?”
- Question subject on metformin compliance.

6.3.5. Day 2 - MAD

On Day 2, after an overnight fast of at least 10 hours, the following procedures will be completed:

- Assess symptoms by spontaneous reporting of adverse events and by asking the subjects to respond to a non-leading question such as “How do you feel?”
- Assess patency of peripheral IV (PIV)/heplock, in accordance with site policies,

- If no longer patent remove and insert a new PIV/heplock in accordance with site policies. Allow subject to rest at least 1 hour prior to obtaining vital signs.
- Complete 24 hour continuous blood pressure monitoring.
 - NOTE: Before proceeding with any other Day 2 assessments, immediately upload the ABPM data to the vendor to determine if the data passes vendor QC. If the data fails technical QC, immediately restart/repeat the ABPM on Day 2 to ensure a complete dataset is obtained. Then start the remaining Day 2 procedures. If the 24 hour ambulatory blood pressure monitoring cannot be repeated on Day 2 please contact the sponsor to discuss alternative times.
- Conduct full physical exam.
- Obtain fasting weight.
- Collect blood sample for pharmacokinetic analysis at 24 hours after Day 1 dosing.
- Collect blood samples for FPG and fasting glucagon.
- Collect fasting blood and urine samples for safety laboratory tests 24 hours after Day 1 dosing.
- Obtain triplicate 12-lead ECG measurements 24 hours after Day 1 dosing.
- Assess temperature, supine pulse and triplicate supine blood pressure 24 hours after Day 1 dosing. Blood pressure is the only vital sign to be collected in triplicate.
- Assess injection site for reactions if necessary (required if a reaction was observed on Day 1).
- Record concomitant medications.
- Question subject on metformin compliance.

6.3.6. Day 3 - MAD

On Day 3, after an overnight fast of at least 10 hours, the following procedures will be completed:

- Assess symptoms by spontaneous reporting of adverse events and by asking the subjects to respond to a non-leading question such as “How do you feel?”
- Assess patency of peripheral IV (PIV)/heplock, in accordance with site policies,
 - If no longer patent remove and insert a new PIV/heplock in accordance with site policies. Allow subject to rest at least 1 hour prior to obtaining vital signs.

- Obtain fasting weight.
- Obtain temperature, supine pulse and triplicate supine blood pressure. Blood pressure is the only vital sign to be collected in triplicate.
- Collect blood samples for pharmacokinetic analysis 48 hours after Day 1 dosing.
- Collect blood samples for FPG and fasting glucagon.
- Record concomitant medications.
- Question subject on metformin compliance.
- Remove PIV/heplock prior to discharge.

If a subject has any clinically significant, study-related abnormalities at the conclusion of a scheduled inpatient portion of the study, the Pfizer medical monitor (or designated representative) should be notified and the subject may be asked to remain in the Clinical Research Unit until such abnormalities are deemed not clinically significant, or it is safe for outpatient follow-up. If the subject is unable or unwilling to remain in the Clinical Research Unit and/or when outpatient follow-up is deemed appropriate, the Pfizer medical monitor (or designated representative) should be so notified, and the investigator should make every effort to arrange follow-up evaluations at appropriate intervals to document the course of the abnormalities.

6.3.7. Day 6 – MAD

Subjects will be admitted to the Clinical Research Unit. Subjects will be required to stay in the Clinical Research Unit for 2 nights and will be discharged on Day 8.

Site staff will review adverse events, concomitant medications, metformin compliance and confirm contraception method. Concomitant medications will be recorded in medication history. Any noted adverse events will be recorded as prior medical history.

- PIV/heplock may be placed, in accordance with site policies, for serial blood collections on Day 7 and 8.

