5.4. Concomitant Medication(s)

Sporadic use of any homeopathics or nutritional supplements should be discouraged as they may confound interpretation of study treatment results. Subject may be on dietary supplement or herbal medicine as long as dose is stable within 2 weeks of screening and throughout the duration of the study.

All concomitant medications taken during the study must be recorded with indication, daily dose, and start and stop dates of administration. All subjects will be questioned about concomitant medication at each clinic visit.

Medications taken within 28 days before the first dose of study medication will be documented as a prior medication. Medications taken after the first dose of study medication will be documented as concomitant medications.

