8. ADVERSE EVENT REPORTING

8.1. Adverse Events

Adverse events will be collected from the time a subject signs consent to the last visit. All observed or volunteered AEs regardless of treatment group or suspected causal relationship to the investigational product(s) will be reported as described in the following sections.

For all AEs, the investigator must pursue and obtain information adequate both to determine the outcome of the AE and to assess whether it meets the criteria for classification as a serious adverse event (SAE) requiring immediate notification to Pfizer or its designated representative. For all AEs, sufficient information should be obtained by the investigator to determine the causality of the AE. The investigator is required to assess causality.

Follow-up by the investigator may be required until the event or its sequelae resolve or stabilize at a level acceptable to the investigator, and Pfizer concurs with that assessment.

As part of ongoing safety reviews conducted by the Sponsor, any non-serious adverse event that is determined by the Sponsor to be serious will be reported by the Sponsor as a SAE. To assist in the determination of case seriousness further information may be requested from the investigator to provide clarity and understanding of the event in the context of the clinical study.

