8.2. Reporting Period

For SAEs, the active reporting period to Pfizer or its designated representative begins from the time that the subject provides informed consent, which is obtained prior to the subject's participation in the study, ie, prior to undergoing any study-related procedure and/or receiving investigational product, through and including 28 calendar days after the last administration of the investigational product. Serious adverse events occurring to a subject after the active reporting period has ended should be reported to the Sponsor if the investigator becomes aware of them; at a minimum, all serious events that the investigator

believe have at least a reasonable possibility of being related to investigational product are to be reported to the Sponsor.

Treatment emergent AEs (serious and non-serious) should be recorded on the CRF/DCT from the time the subject has taken at least one dose of study treatment through last subject visit.

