8.8. Causality Assessment

The investigator's assessment of causality must be provided for all AEs (serious and non-serious); the investigator must record the causal relationship in the CRF/DCT, as appropriate, and report such an assessment in accordance with the serious adverse reporting requirements if applicable. An investigator's causality assessment is the determination of whether there exists a reasonable possibility that the investigational product caused or contributed to an AE; generally the facts (evidence) or arguments to suggest a causal

relationship should be provided. If the investigator does not know whether or not the investigational product caused the event, then the event will be handled as “related to investigational product” for reporting purposes, as defined by the Sponsor (see Section on [Reporting Requirements](#)). If the investigator's causality assessment is “unknown but not related to investigational product”, this should be clearly documented on study records.

In addition, if the investigator determines that an SAE is associated with study procedures, the investigator must record this causal relationship in the source documents and CRF/DCT, as appropriate, and report such an assessment in accordance with the SAE reporting requirements, if applicable.

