8.13.2. Non-Serious Adverse Event Reporting Requirements

All AEs will be reported on the AE page(s) of the CRF/DCT. It should be noted that the form for collection of SAE information is not the same as the AE CRF/DCT. Where the same data are collected, the forms must be completed in a consistent manner. For example, the same AE term should be used on both forms. AE should be reported using concise medical terminology on the CRFs/DCTs as well as on the form for collection of SAE information.

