8.2.3. Adverse Events

The incidence of adverse events will be summarized, for all adverse events (overall), for adverse events by relation to treatment, and adverse events by severity. The summaries will be prepared using Pfizer standards. The incidence of adverse events will be summarized by count of subject incidence. Any events observed following start of treatment or worsening in severity will be counted as treatment emergent.

The following parameters will be summarized:

- Incidence, severity and causal relationship of treatment emergent AEs (TEAEs).
- Incidence and severity of hypoglycemic events.
- Incidence of abnormal laboratory findings.

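### Four post-dose MAD admissions tell sites to file adverse events as medical history, against Protocol Section 8 and SAP 8.2.3

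*Protocol*

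**What the plan says.** MAD dosing starts on Day 1; the Q4-week schedule repeats it on Days 29 and 57 (Protocol 3.1). For the inpatient admissions on Days 6, 27, 62 and 83, the visit text asks staff to review medications and adverse events and then gives two filing instructions: "Concomitant medications will be recorded in medication history" and "Any noted adverse events will be recorded as prior medical history". The same adverse-event sentence stands at the two pre-dose admissions, SAD Day -2 (6.2.1) and MAD Day -3 (6.3.1).

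Elsewhere the documents give different rules:

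- Protocol 8.1: "Adverse events will be collected from the time a subject signs consent to the last visit".
- Protocol 8.2: "Treatment emergent AEs (serious and non-serious) should be recorded on the CRF/DCT from the time the subject has taken at least one dose", and onward to the last visit.
- Protocol 8.13.2: "All AEs will be reported on the AE page(s) of the CRF/DCT".
- SAP 8.2.3: "Any events observed following start of treatment or worsening in severity will be counted as treatment emergent".
- Protocol 5.4: "Medications taken after the first dose of study medication will be documented as concomitant medications".

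**The concern.** An event first noted at one of these four visits has two incompatible destinations: medical history under Section 6.3, the AE page under Section 8. Incidence, severity and causal relationship of TEAEs are a primary endpoint (Protocol 2.2.1), and Section 8.8 requires a causality assessment for every AE. An event entered only as medical history would not go through that assessment, and the SAP cannot count what never reaches the AE page. Site staff who follow the visit text literally are obeying the protocol, so the misfiling need not show up as a deviation. The SAP describes no reconciliation of post-dose history entries that would catch it.

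The part of the data most exposed is non-serious events first reported at Days 6 and 27. Day 6 also falls before the earliest MAD escalation review in Section 3.3, where severe AEs in the same organ class form one limb of the stopping rule.

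**Working it through.** **Text comparison**

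| Visit | Timing | Filing rule in visit text | Separate AE-assessment bullet at that visit | AEs assessed next day |
|---|---|---|---|---|
| Day 6 (6.3.7) | 5 days after dose 1 | medical history | no | Day 7 |
| Day 27 (6.3.11) | 26 days after dose 1 | medical history | no | Day 28 |
| Day 62 (6.3.19) | 5 days after dose 3 | medical history | yes | Day 63 |
| Day 83 (6.3.24) | 26 days after dose 3 | medical history | yes | Day 84 |

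No passage restricts the sentence to events that began before dosing, and none gives an order of precedence. At the two pre-dose admissions the wording does not touch the treatment-emergent rule. In the MAD schedule, medical history is otherwise collected only at Screening and Day -1. The likely explanation, which is an inference, is that the admission paragraph was copied forward.

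**Exposure** (the plan gives no figure on this point; nominal visit days are used)

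- Time since the previous contact: Day 3 to 6 = 3; Day 15 to 27 = 12; Day 59 to 62 = 3; Day 78 to 83 = 5. Sum: 3 + 12 + 3 + 5 = 23 days.
- Share of Days 1-85: 23/84 = 27.4%. Share of Days 1-169: 23/168 = 13.7%.
- Days 6 and 27 only: 3 + 12 = 15 days; 15/84 = 17.9%; 15/168 = 8.9%.
- Before the earliest 14-day escalation review: only the Day 6 interval, 3/14 = 21.4%.

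These are intervals in which an event could first come to light at an affected visit. They are not rates of loss.

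**Subjects** (SAP Table 2)

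- MAD subjects: (8 + 2) + (16 + 4) + (8 + 2) = 40.
- Subject-admissions: at most 40 × 4 = 160, of which 40 × 2 = 80 are at Days 6 and 27.
- Pooled MAD placebo (pooled within the MAD portion, Protocol 9.6): 2 + 4 + 2 = 8.

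**Effect of one misfiled subject**, if that subject's only TEAE is filed as history and not recovered

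- Group of 8 (50 mg, 150 mg, pooled MAD placebo): 1/8 = 12.5 percentage points.
- 75 mg group of 16: 1/16 = 6.25 percentage points.
- The AE risk difference in SAP 10.2.2 shifts by the same amount: down if the subject is on active drug, up if on placebo.

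Table 10 of the protocol is not used here. It concerns SAEs, which reach the sponsor by a separate route.

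**The case against.** The best reply is that the sentence is a drafting slip with little practical reach. Section 8 is categorical that AEs go on the AE page. Section 8.12 has the investigator report observed and volunteered AEs and question every subject. The visit sentence never says that history replaces the AE page, so a site following both instructions would record twice rather than lose the event. Staff are told to review AEs at all four visits, and the MAD schedule appears to mark AE monitoring there too, although the table is hard to read in the text available. No medical-history collection is scheduled on those days, so a post-dose onset date in history should stand out to a monitor.

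Several relevant event types also have their own channel: SAEs within 24 hours (8.13.1), hypoglycemia on a dedicated form (7.6), injection-site reactions on a dedicated CRF (7.2.12), and ALT or AST at 3 times ULN or more, which must be reported as AEs (8.4). The laboratory, ECG and vital-sign limbs of the escalation rule do not depend on the AE page. The 23-day total includes 8 days (3 + 5) before Days 62 and 83, which have their own AE-assessment bullet.

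All of this stands and lowers the chance of loss. It does not remove the conflict. A site that has already filed an event as history may see no reason to enter it again. A non-serious event that resolved in the 12 days before Day 27 may not surface when the subject is asked on Day 28 about present symptoms. The 15-day figure is the fairer one for the weakest points.

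**Conclusion.** The text is wrong as written at four post-dose visits. It contradicts Protocol 8.1, 8.2 and 8.13.2 and SAP 8.2.3 on adverse events, and Protocol 5.4 on medications. Confidence in the contradiction is high.

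The effect on the data is uncertain: the documents give no misfiling rate, and none is assumed here. The exposure bounds are 15 days at the two weakest visits and 23 days at all four, in the 40 MAD subjects; SAD subjects are unaffected. The 12.5- and 6.25-point shifts require that a subject's only TEAE was misfiled and never recovered. Because a primary endpoint is involved and the check is cheap, this should be fixed, although it does not by itself call the trial's safety conclusions into question.

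**What to change.** **Protocol 6.3.7, 6.3.11, 6.3.19 and 6.3.24.** Replace the two filing sentences with, for example: *AEs noted since the previous visit are entered on the AE page (Sections 8.2 and 8.13.2), and medications are documented as concomitant (Section 5.4).* Keep the medical-history wording only at SAD Day -2 and MAD Day -3.

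**Before database lock.** The SAP already lists the final MAD cohorts, so this is now the step that matters most. Query all MAD medical-history and medication-history entries with an onset or start date on or after first dose. Have the site re-enter confirmed events on the AE page with severity and causality, and reclassify the medications. If nothing was misfiled, the query documents that.

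**SAP 8.2.3.** Add one line stating that this reconciliation is completed before lock and that the number of entries moved is reported.

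The cost is wording in four protocol sections, one SAP line and one data-management query. No visits or procedures are added.
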